### Pharmacokinetic parameter estimation:

Definition and estimation of PK parameters are described below. PK parameters will be determined from the levels of VHH from PK analysis set for both Part A and Part B subjects. PK parameters will be determined for each subject by non-compartmental analysis using Phoenix WinNonlin software (version 8.1 or higher). The following parameters (but not limited to) will be derived, where appropriate from the individual concentration versus time profiles of VHH.

Parameter	Definition
-----------	------------

$C_{max}$	Maximum observed peak VHH concentration following administration of the initial dose and a course of treatment if systemic absorption is observed
-----------	---

$C_{last}$	Last observed concentration, obtained directly from concentration data
------------	--

$AUC_{0-t}$	The area under the concentration-time curve, from 0 (time of Dosing) to the last time point with measurable analyte concentration following administration of the initial dose and a course of treatment if systemic absorption is observed, calculated by the linear up and the log down trapezoidal method calculated as:
-------------	---

$$AUC(t_1 - t_2) = \sum_{t_1}^{t_2} \frac{(C(t_1) + C(t_2))}{2} * (t_2 - t_1)$$

$AUC_{0-inf}$	Area under the concentration-time curve extrapolated to infinite time calculated as
---------------	---

$$AUC_{0-inf} = AUC_{0-t} + \frac{C_{last}}{\lambda_z}$$

$t_{max}$	Time to reach $C_{max}$ following administration of the initial dose and a course of treatment if systemic absorption is observed. If the maximum observed concentration value occurs at more than 1 time point, $t_{max}$ is defined as the first time point with this value.
$\lambda_z$	Apparent first order terminal elimination rate constant, estimated using the negative slope of the least square regression analysis of the log concentration versus time data for the terminal linear portion of the curve.
$t_{1/2}$	Terminal elimination half-life computed as

$$t_{1/2} = \frac{\ln(2)}{\lambda_z}$$

Actual sampling times will be used for the PK analysis and if the actual sampling time is not recorded, the nominal sampling time will be used.

All concentration values reported as no results (not collected or not determined) values will be treated as missing. For the calculation of concentration summaries, all concentrations below the quantifiable limit (BLQ) will be treated as 0 except for geometric statistics (geometric mean and geometric CV%). For the purpose of calculating PK parameters and plotting mean and individual concentration-time profiles, BLQ values will be treated as 0 prior to the first quantifiable concentration. After the first measurable concentration, subsequent BLQ values are treated as missing.

Summary statistics (n, nBLQ, mean, standard deviation [SD], coefficient of variation [CV%], median, minimum, maximum, geometric mean, geometric SD, and geometric CV%) will be calculated for each time point. Geometric mean, SD, CV% are only for PK parameter summaries.

Pharmacokinetic parameters for VHH will be listed and summarized descriptively, including n, arithmetic mean, SD, minimum, median, maximum, coefficient of variation [CV(%)], geometric mean (GM), geometric SD, geometric CV%; geometric CV% calculated as the square root of the exponentiated SD of the natural log transformed data ( $\text{SQRT}(\exp(\ln^2)-1)$ ), where appropriate. For  $t_{max}$ , only n, minimum, median, and maximum will be reported.

When reporting individual values and descriptive statistics for PK concentrations of VHH, the following rules will apply regarding rounding and precision:

- Individual values for PK concentration data will be reported to the same level of precision as received from the bioanalytical laboratory.
- Descriptive statistics for PK concentration data will be reported to the same level of precision as the individual data for the minimum and maximum, and to 1 additional decimal place or 1 additional significant figure— depending on the reporting format of the original data with a maximum of 4 significant digits - for the mean (arithmetic and geometric), median and SD. The 95% CI for the geometric mean will use 1 decimal place more, or 1 significant figure more – depending on the reporting format of the original data – than the value around which the confidence interval is constructed.
- Geometric CV will be reported as a percentage to 1 decimal place.

When reporting individual values and descriptive statistics for PK parameters the following rules will apply with regard to rounding and precision:

- Individual values for PK parameters will be reported to 3 significant figures.
- Descriptive statistics for PK parameters should be rounded to 4 significant figures for the mean, median and SD and to 3 for the others.
- Data listings containing all documented data and all derived data will be generated.
- Missing data will not be imputed.

### **9.1 Biostatistical methods**

The levels of VHH will be listed for all timepoints collected. Concentrations will be summarized for all scheduled timepoints by study part, per dose cohort and total. Timepoints will be calculated and listed in terms of study days elapsed following initial dose and will be employed for determination of area under the concentration time curve rather than the nominal study timepoint.

The area under the VHH concentration-time curve, from time  $t_1$  to  $t_2$  hours where the values of  $t_1$ - $t_2$  are:

#### Part A

- Pre-dose to 2 hours after the initial dose.
- Pre-dose to 24 hours post initial dose

#### Part B

- Pre-dose to 2 hours after the initial dose.
- Pre-dose to day 29 post initial dose.

Figures representing mean  $\pm$  SE (standard error) will be included for VHH concentrations and percentage change from baseline of Part A, Part B: Cohorts 1, 2, 3 and Part B: Placebo.

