2 PREVIOUS EXPERIENCE WITH LMN-101

2.1 LMN-101 Drug Product

Lumen developed SP1182, a strain of spirulina (*Arthrospira platensis*) that has been stably engineered by chromosomal integration to constitutively express a protein that binds and inhibits the FlaA filament protein on the flagellum of *C. jejuni*. The drug, LMN-101, is orally delivered whole, dried spirulina biomass in capsule form (i.e., the active biologic is not purified from the spirulina biomass). After spray drying, the spirulina powder is non-viable (likely due to the elevated temperature achieved during drying and the low water content of the resulting powder) while the binding activity of the campylobacter binding protein is retained.

The aa682 campylobacter binding protein is constitutively expressed as a soluble protein that remains in the cytosol (not secreted or displayed on the surface of the cell). It is a simple yet highly specific binding protein that is derived in part from the variable binding domain of a llama single-domain antibody (also known as a "VHH") that has been modified for proteolytic stability. For clarity, the binding protein is monomeric and does not contain many of the complex effector functions of conventional antibodies: it does not contain an Fc domain; it is comprised of a single polypeptide chain; it is not glycosylated; and it does not contain multiple disulfide bonds. It binds

to and inhibits a campylobacter flagellin protein whose sequence does not contain any homology to known human proteins and has been demonstrated to lack cross reactivity to a broad panel of human tissues. The aa682 binding protein is engineered as a fusion with *E. coli* maltose binding protein (MBP), which is a chaperone that increases solubility, bioactivity, and expression level in spirulina. MBP is present in all humans as an abundant component of the normal gastrointestinal commensal flora.

Spirulina (a type of blue-green algae) was selected as the expression host because it is Generally Recognized as Safe (GRAS) under FDA regulations, has a well-understood and non-toxic safety profile from its wide use as a food source for humans and animals, has been involved in numerous clinical trials with no reports of AEs, and is highly stable as a spray-dried powder.

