#### **4.1.2 Pharmacokinetic (PK) Analysis Set**

The PK analysis set will be defined as a per Protocol population which consists of all randomized subjects who complete the full course of study drug and who have an adequate quantifiable and interpretable serum concentrations of VHH. Subjects with protocol violations to be assessed on a subject-by-subject basis for inclusion in the PK Population. The sponsor will confirm the eligibility of subjects after a review of the serum concentrations data of VHH. Patients who receive only placebo will be excluded from the PK set. PK parameters will be excluded from the analysis and summary statistics where there are inadequate serum concentrations of VHH. PK analysis of serum VHH will be conducted using the Pharmacokinetic analysis set.

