**Programming Note:**

- Include all treatment groups: Part A: LMN-101 3000 mg, Part B: LMN-101 300 mg, Part B: LMN-101 1000 mg, Part B: LMN-101 3000 mg.
- Include all scheduled visits/time points.

Program: filepath\_name, Output Name: filepath\_name Creation Date/Time: DDMMYYYY HH:MM

Page 1 of xx

Sponsor: Lumen Bioscience, Inc.

Database Lock: yyyy-mm-dd

Protocol: CAM01

Table 14.2.1.2 Summary of PK Parameters (PK Analysis Set)

Parameter: Cmax at Day 1: 2h post dose

Treatment Group Visit	n	Mean	SD	Median	Minimum	Maximum	%CV	GM	GSD	%GCV	Geometric 95% CI Mean
Part A: LMN-101 3000 mg (N=xx)	xx	xx.x	xx.x	xx.x	xx	xx	xx.x	xx.x	xx.x	xx.x	xx.x, xx.x
Part B: LMN-101 300 mg (N=xx)	xx	xx.x	xx.x	xx.x	xx	xx	xx.x	xx.x	xx.x	xx.x	xx.x, xx.x
Part B: LMN-101 1000 mg (N=xx)	xx	xx.x	xx.x	xx.x	xx	xx	xx.x	xx.x	xx.x	xx.x	xx.x, xx.x
Part B: LMN-101 3000 mg (N=xx)	xx	xx.x	xx.x	xx.x	xx	xx	xx.x	xx.x	xx.x	xx.x	xx.x, xx.x

etc.

SD: Standard Deviation; CV: Coefficient of Variation; Cmax: Peak VHH Concentration**Programming Note:**

- Include all PK Parameters: Cmax at Day 1: 2h post dose, Cmax after Day 1, Tmax, λz, t1/2, AUC0-2hr, AUC0-course, AUC0-inf
- For all parameters other than tmax; n, mean, SD, median, minimum, maximum, %CV, Geometric mean, geometric SD, geometric CV% and geometric 95% CI.
- For tmax, only n, minimum, median, and maximum will be reported.

Program: filepath\_name, Output Name: filepath\_name Creation Date/Time: DDMMYYYY HH:MM

Page 1 of xx

Sponsor: Lumen Bioscience, Inc.  
 Protocol: CAM01

Database Lock: yyyy-mm-dd

Table 14.3.1.1 Summary of Concomitant Medication (Safety Analysis Set)

Anatomic Therapeutic Classification (ATC) Preferred Term (PT)	Part A:		Part B:		LMN-101 Overall (N=xx) n (%) m	Placebo (N=xx) n (%) m	Overall (N=xx) n (%) m
	LMN-101 3000 mg (N=xx)	LMN-101 300 mg (N=xx)	LMN-101 1000 mg (N=xx)	LMN-101 3000 mg (N=xx)			
	n (%) m	n (%) m	n (%) m	n (%) m			
Subjects with at least one Concomitant Medication	xx (xx.x%) xx	xx (xx.x%) xx	xx (xx.x%) xx	xx (xx.x%) xx	xx (xx.x%) xx	xx (xx.x%) xx	xx (xx.x%) xx
ATC1	xx (xx.x%) xx	xx (xx.x%) xx	xx (xx.x%) xx	xx (xx.x%) xx	xx (xx.x%) xx	xx (xx.x%) xx	xx (xx.x%) xx
PT1	xx (xx.x%) xx	xx (xx.x%) xx	xx (xx.x%) xx	xx (xx.x%) xx	xx (xx.x%) xx	xx (xx.x%) xx	xx (xx.x%) xx
PT2	xx (xx.x%) xx	xx (xx.x%) xx	xx (xx.x%) xx	xx (xx.x%) xx	xx (xx.x%) xx	xx (xx.x%) xx	xx (xx.x%) xx

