## Listing 16.2.6.1 PK Serum Sample Collection Times (PK Population)

Cohort/Treatment: Part A: LMN-101 3000mg

Subject ID	Sampling Timepoint	Was PK Sample Collected?	Actual Time (h) 	PK Sample Collection Date and Time (YYYY-MM-DD HH:MM)	Day 1 Study Drug Administration Date and Time (YYYY-MM-DD HH:MM)	Comments
XXX-XXX	Day 1 Pre-dose	Yes	xx.xx	YYYY-MM-DD HH:MM	YYYY-MM-DD HH:MM	
	Day 1 2h Post-dose	Yes	xx.xx	YYYY-MM-DD HH:MM	YYYY-MM-DD HH:MM	
	Day 2	Yes	xx.xx	YYYY-MM-DD HH:MM	YYYY-MM-DD HH:MM	
XXX-XXX	Day 1 Pre-dose	Yes	xx.xx	YYYY-MM-DD HH:MM	YYYY-MM-DD HH:MM	
	Day 1 2h Post-dose	Yes	xx.xx	YYYY-MM-DD HH:MM	YYYY-MM-DD HH:MM	
	Day 2		xx.xx	YYYY-MM-DD HH:MM	YYYY-MM-DD HH:MM	
Etc						

Relative to date and time of study drug administration on Day 1

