**Programming Note:**  
 The x-axis will represent elapsed days after initial dosing [0 to 1];  
**label:** "Time (Days)"; vertical dashline to be added on Dosing (Day=0) to indicate Baseline.  
 The y-axis will represent the mean serum concentrations of VHH (unit) per treatment group. Whiskers will be included to reflect the SEs;  
**label:** "Mean VHH (SE) Concentration (unit)".

The y-axis will be on the linear scale.  
 Treatment groups to be included are Part A: LMN-101 3000 mg, Part B: LMN-101 300 mg, Part B: LMN-101 1000 mg, Part B: LMN-101 3000 mg. All treatment groups will be represented on a single page. Each treatment group will be presented as a distinct line type.

Sponsor: Lumen Bioscience, Inc.  
Protocol: CAM01

Database lock: yyyy-mm-dd

Figure 14.2.1.2 Log10Mean (+/-SE) Serum Concentrations of VHH by Day - Baseline to Day 2 (24hrs) (PK Population)

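### SAP 9.1 promises VHH figures that include Part B placebo, but the PK analysis set and the output shells leave placebo out, so the post-dose control may be missing from the reported serum concentrations

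*SAP*

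**What the plan says.** SAP 9.1, under Part B, commits to mean ± SE figures of VHH concentration and "percentage change from baseline of Part A, Part B: Cohorts 1, 2, 3 and Part B: Placebo".

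SAP 4.1.2 defines the PK analysis set differently. It states that "Patients who receive only placebo will be excluded from the PK set" and that "PK analysis of serum VHH will be conducted using the Pharmacokinetic analysis set". The same definition also asks for completion of the full course and for adequate quantifiable concentrations.

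SAP sections 17 to 19 assign both PK tables, all four listings under the pharmacokinetic heading and all eight figures to this set. The shells follow it:

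- The programming note to mock Table 14.2.1.1 (serum concentrations) reads: "Include all treatment groups: Part A: LMN-101 3000 mg, Part B: LMN-101 300 mg, Part B: LMN-101 1000 mg, Part B: LMN-101 3000 mg". There is no placebo row.
- The notes to the mean figures (14.2.1.1 to 14.2.1.4) read: "Treatment groups to be included are Part A: LMN-101 3000 mg, Part B: LMN-101 300 mg, Part B: LMN-101 1000 mg, Part B: LMN-101 3000". The notes to the individual figures (14.2.2.1 to 14.2.2.4) and the general group list for the figures name the same four groups.
- The note to Listing 16.2.6.3 (individual parameters) names those four groups as the make-up of the PK set.
- The notes to Listings 16.2.6.1 (sampling times) and 16.2.6.2 (individual concentrations) name no groups. Placebo is excluded there only because the titles say PK Population.

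Other SAP text points the other way. Section 9 undertakes to list all PK data collected, section 9.1 undertakes to list VHH levels at every timepoint collected, and the general comments to the mock listings give a placebo heading for each of the three Part B cohorts.

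**The concern.** Leaving placebo out of Cmax, AUC and half-life is sensible, because there is no dose to describe. Raw concentrations are different: there, placebo is the control.

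The PK question in this trial is first a qualitative one. Protocol 2.1 describes the active protein as a 55 kDa molecule that is not expected to reach the circulation, and Protocol 3.4 gives the detection of any absorption as the reason for measuring serum levels. The answer also decides what happens next, since PK analysis (SAP 9) and anti-drug antibody testing (SAP 13 and 15.1) depend on absorption being observed. The documents set no threshold for that judgement. If a few low values appear after LMN-101, the reader will want to know whether similar values appear after wild-type spirulina taken on the same schedule. Protocol 6.1 makes placebo exactly that comparison.

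**Working it through.** **Inputs**

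- Part A: 2 participants, all on LMN-101 (Protocol 4.1).
- Part B: 3 cohorts, each with 4 on LMN-101 and 2 on placebo (Protocol 4.1).
- Serum PK samples per Part A participant: pre-dose, 2 h and 24 h, which is 3 (Protocol Table 3, PK footnote).
- Serum PK samples per Part B participant: the same three plus Days 8, 28 and 29, which is 6, with no distinction by arm (Protocol Table 4, PK footnote).

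**Reproducing the plan's own count**

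2 + 3 × (4 + 2) = 20 participants, as stated. Part B has 3 × 4 = 12 on LMN-101 and 3 × 2 = 6 on placebo.

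**Scheduled serum PK samples**

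| Group | Calculation | Samples | Of which post-dose |
|---|---|---|---|
| Part A LMN-101 | 2 × 3 | 6 | 2 × 2 = 4 |
| Part B LMN-101 | 12 × 6 | 72 | 12 × 5 = 60 |
| Part B placebo | 6 × 6 | 36 | 6 × 5 = 30 |
| Total | | 114 | 94 |

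Under the set definition and shells, at most 6 + 72 = 78 samples can be shown. The figure is a ceiling because the PK set also requires a full course and quantifiable levels. The 36 placebo samples have no place. They are 36 / 114 = 31.6% of all scheduled serum PK samples and 36 / 108 = 33.3% of those in Part B.

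**Outputs compared with the text**

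| Output | Assigned to PK set | Placebo named in its shell |
|---|---|---|
| Tables 14.2.1.1 and 14.2.1.2 | 2 of 2 | 0 of 2 |
| Listings 16.2.6.1 to 16.2.6.4 | 4 of 4 | 0 of 4 |
| Figures 14.2.1.1 to 14.2.2.4 | 8 of 8 | 0 of 8 |
| Percentage change in VHH (SAP 9.1) | no shell exists | not applicable |

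A programmer who follows SAP 9.1 must draw a placebo line. One who follows SAP 4.1.2 and the figure notes must not.

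**What background is available without placebo**

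Every LMN-101 participant has a Day 1 pre-dose sample: 2 + 12 = 14 samples, which have their own row in Table 14.2.1.1 with n and nBLQ. These show background before any capsule is taken. They cannot show an effect of the spirulina carrier or a change during the 28 days of dosing. Only the 30 post-dose placebo samples can do that.

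**The case against.** Several things can fairly be said on the other side.

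- A reader might infer that placebo values will never appear in the report. The documents do not go that far. SAP 9 and 9.1 undertake to list all PK data, and the general listing headings include placebo. Those statements are in tension with the PK Population titles of Listings 16.2.6.1 and 16.2.6.2 and do not settle the matter. The shells also carry leftover text from another study (another compound's dose groups, and uric acid in a figure note), so they are weak evidence of a deliberate decision to drop the control.
- A reader might infer that without placebo the report could show nothing about background. The pre-dose rows, and to a degree the three dose levels, do give some information. What is lost is narrower: the control for the carrier and for time.
- A reader might point to Protocol 2.1, which says that "MBP is present in all humans as an abundant component of the normal gastrointestinal commensal flora", and infer cross-reactivity, since the drug is a fusion with that protein. Nothing in the documents says that the serum assay detects MBP or that commensal MBP reaches serum, so the point does not rest on this.
- A reader might want a probability of false positives. No assay error rate is given, so none is offered here.
- That placebo samples are assayed is an inference. Protocol 7.4 says that serum is stored. Protocol 3.4 and 7.18 and SAP 9 say without restriction by arm that VHH levels will be determined, and SAP 9.1 expects placebo to be plotted, so assay is likely but not stated.
- The interim spreadsheet in SAP 15.1 may contain placebo values. It is blinded to treatment and is not a report output, so it cannot show background by arm.

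The contradiction between SAP 9.1 and SAP 4.1.2 with its figure shells survives all of these.

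**Conclusion.** The SAP contradicts itself on whether placebo is shown in the VHH concentration figures, and the more detailed instructions leave it out. If they are followed, up to 36 scheduled placebo samples of 114 (31.6%), 30 of them post-dose, are absent from every PK output. They would otherwise stand beside 60 post-dose Part B LMN-101 samples. The counts assume full enrolment, every scheduled sample taken, and placebo samples assayed.

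The consequence is limited. Serum PK is a descriptive secondary endpoint, conditional on absorption, and the primary safety analysis is untouched. The point should still be fixed, because low positives in the LMN-101 groups would be hard to read as absorption without the only control for carrier and time.

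**What to change.** 1. Keep the PK set, without placebo, for derived parameters (Table 14.2.1.2 and Listing 16.2.6.3).
2. Report raw VHH concentrations for all participants with a VHH result in Table 14.2.1.1, Listings 16.2.6.1 and 16.2.6.2 and the concentration figures, with a Part B placebo group. In the table, give n and nBLQ for placebo at each visit. Placebo in the figures is what SAP 9.1 already promises; the table and listing rows are a small extension of it.
3. Amend SAP 4.1.2, the analysis-set columns in sections 17 to 19 and the programming notes to match.
4. State explicitly that placebo serum samples are assayed.
5. Either add a shell for percentage change from baseline in VHH or delete it from SAP 9.1. The SAP 3.2 formula divides by baseline, so it cannot be computed where the pre-dose result is below the quantification limit, whether that result is set to zero or treated as no valid baseline.

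The cost is SAP wording and one more group in existing outputs. No visit or blood draw is added. If placebo samples are not currently due to be assayed, up to 36 further determinations would be needed.

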## **10. PHARMACODYNAMICS (PD)**

Not applicable

## **11. EFFICACY**

Not applicable

## **12. SAFETY**

Safety endpoints will be analysed using the safety analysis set. TFLs will be presented as specified in section 3.1 by treatment group.

### **12.1 Adverse Events**

#### **12.1.1 Endpoints**

- AE
- SAE
- TEAE

AEs and SAEs are defined in the study protocol. TEAEs are defined as adverse events that occurred or worsened following the first administration of study medication.

All AEs will be coded using MedDRA. AE summaries will be restricted to TEAEs only.

Summary tables will include the number of participants (%) experiencing an event and the number of events. Participants will be counted only once at each SOC and PT level of summary.

The TEAE summaries will include:

- Overall Summary of TEAEs
  - Number of TEAEs
  - Number of TEAEs with Toxicity  $\geq$  Grade 3
  - Number of Serious TEAEs
  - Number of Study Drug Related TEAEs (Drug Related: A Possibly or Probably related TEAE)
  - Number of TEAEs leading to study withdrawal
- TEAE and SAE summary by SOC and PT
  - TEAEs
  - Treatment Emergent SAEs
  - TEAE by relationship to Study Drug
  - TEAE summary by Toxicity Grade

All AEs will be listed and will include verbatim term, PT, SOC, treatment group, relationship to study drug, toxicity grade, seriousness, reason for serious event, outcome, and action taken with regards to the study drug and AE. Separate listings will be created for SAEs and events leading to study drug withdrawal.

### **12.2 Concomitant medication**

Prior medication will be defined as any medication stopped prior to the first dose of study drug.

Concomitant medications will be summarized by ATC class Level 3 and PT. Within each category, the number of participants who used the medication (count and percentage) will be presented. Participants who used the same medication on multiple occasions will only be counted once in the specific category (PT). PTs will be sorted alphabetically. In addition to the summaries by the coded terms, the number of participants who used at least one concomitant medication during the study will be presented.

All information that was collected on the Concomitant Medication eCRF as well as the coded WHO-DD terms will be included in the listings.

Prior medications will be listed only.

